8.12 Pharmacokinetic Studies

During the phase 1 component of the study, blood samples after specific infusions during Run-in Cycle and Cycle 2 of SL-401 will be used to determine plasma concentrations of SL-401. The concentration of SL-401 in plasma samples will be determined by a sensitive and specific sandwich enzyme-linked immunosorbent assay (ELISA) method at a contract laboratory according to industry GLP bioanalytical practices. Plasma concentration data over time will be used to characterize the PK disposition of SL-401, to assess any change in the PK properties of SL-401 during the 5-day course of treatment or between cycles of treatment, and relate the PK characteristics of SL-401 to immunogenicity, toxicity, and disease activity.

Collectively, the SL-401 plasma concentration-time data will be analysed by conventional noncompartmental PK methods to define the fundamental PK properties of SL-401. Furthermore, if supported by the adequacy of the data, a population PK model will be developed, in which the effects of various potentially relevant co-variants (i.e., gender, age, IL-3R expression, immunogenicity) on relevant PK parameters, will be evaluated. Sample collection requires that the actual date and time (24-hour clock) that the SL-401 treatment begins (start of infusion) and ends (end of infusion) will be recorded as will be the date and time (24-hour clock time) of all blood samples.

Detailed instructions for collecting, processing, storing, and shipping the samples are provided in a separate procedure manual. PK sample aliquots will be shipped either to MRL or directly to the EMD Millipore Corporation/Eurofins Pharma Bioanalytical Services US Inc. and evaluated.

Blood samples will be collected into ethylenediaminetetraacetic acid (EDTA) tubes (lavender top, at least 6 mL each); upon collection the samples should be inverted gently several times to ensure adequate mixing of the EDTA anticoagulant and whole blood. Within approximately 30 minutes of collection, samples should be centrifuged in a refrigerated centrifuge to separate the plasma. An aliquot of the plasma (> 1 mL) will be transferred to a clean tube, tightly sealed, labelled appropriately and stored frozen at -70°C or below prior to analysis in the validated immunoassay.

Samples will be collected immediately prior to the start of the infusion of SL-401, immediately after end of infusion (time recorded), then 15, 30, 45, 60, 90, 120, 180, and 240 minutes after the completion of the infusion (see Table 14). It is recognized that it is not always possible to obtain the specimens at the precise time points specified above, although it requested that sites make every effort to do so; it is essential that the precise time of infusion and times of subsequent pharmacokinetic sampling be recorded diligently.

The nominal blood sampling time schedule is summarized in Table 14 for the following SL-401 treatment days:

- Cycles Run-in Cycle and Cycle 2, infusion 1 (i.e., Day 1).
- Cycles Run-in Cycle and Cycle 2, infusion 5 (i.e., usually Day 5).

8.13 Immunogenicity Studies

Peripheral blood samples (10 mL) will be collected (serum red top tube, no additive) for the detection and characterization of SL-401 reactive antibodies according to the following schedule:

 Run-in Cycle: Day 1 (pre-infusion) and Day 5 (pre-infusion), Day 1 of each subsequent cycle (pre-infusion) and at the EOT visit.

- If infusions are held (postponed) for any reason, an immunogenicity sample must be collected within 3 ± 3 days after completion of the last SL-401 infusion for the cycle.
- If there are clinical manifestations suggesting either an infusion related reaction or drug hypersensitivity, an immunogenicity sample should be obtained, as indicated in Section 7.7.3.1.

Samples for immunogenicity assessment will be shipped to MRL, and will subsequently be evaluated by the EMD Millipore Corporation/Eurofins Pharma Bioanalytical Services US Inc. Detailed instructions for collecting, processing, storing, and shipping the samples will be provided in a separate procedure manual.

In the setting of detection of SL-401 reactive antibodies, plasma from corresponding specimens will be evaluated for SL-401 levels (PK analysis). Plasma from patients without SL-401 reactive antibodies would then be utilized as a control for this pharmacokinetic analysis.

Following the required immunogenicity and PK evaluations, if additional serum or plasma is available, this serum and/or plasma may be used for evaluation of other relevant markers (for example IL-3 levels) if considered appropriate by the Sponsor or Investigator.

9 Schedule of Events

The study schedule of events is summarized in Table 13.

9.1 Day -21 to -1: Screening

The following evaluations will be performed on Day -21 to -1 to determine the patient's eligibility for the study and in anticipation of study drug:

- Informed Consent and registration in POMALYST REMS system.
- Inclusion / Exclusion criteria review.
- Medical and MM history, including prior therapy and concomitant medications.
- Physical examination.
- ECOG performance status.
- Vital signs, height and weight.
- 12-lead ECG.
- ECHO or MUGA scan.
- Urine or serum pregnancy (see Section 8.9 and Table 13).
- Clinical laboratory tests: hematology, serum chemistry.
- PT / INR, aPTT.
- Urinalysis.
- Plasmacytoma evaluation.
- Skeletal survey.
- Bone marrow aspiration and biopsy (biopsy required for correlative samples).
- Peripheral blood (whole blood, serum, plasma) for correlative studies.
- MM-specific laboratory tests.
- AE and SAE monitoring (baseline signs and symptoms).
- Prior and ongoing medications.

Investigators will maintain a confidential log of all patients who have been screened for participation in the study whether or not the patient was eligible for study participation.

9.2 Run-in Cycle

- 9.2.1 Days 1 5 (Up to Day 10 if infusion[s] held): Pre-infusion
 - Inpatient admission (Day 1).
 - ECOG performance status (Day 1 only).
 - Physical examination (complete physical examination on Day 1; symptom-directed on other days, as warranted).
 - Vital signs and weight.
 - Clinical laboratory tests: hematology, serum chemistry.
 - Urinalysis (Day 1 only).
 - Collection of peripheral blood for immunogenicity (serum) Pre-infusion (on Days 1 and 5 only).
 - MM-specific laboratory tests (Day 1 only).
 - PK sampling (infusions 1 and 5) prior to and following infusion.
 - Diphenhydramine 50 mg IV 60 minutes prior to infusion.
 - Acetaminophen 650 mg PO 60 minutes prior to infusion.
 - Methylprednisolone 50 mg IV (or an equivalent dose of another corticosteroid)
 60 minutes prior to infusion.
 - Ranitidine 50 mg IV (or an equivalent doses of another H₂-histamine antagonist)
 60 minutes prior to infusion.
- 9.2.2 Days 1 5 (Up to Day 10 if infusion(s) held): During/Post Infusion
 - Collection of peripheral blood for PK sampling (infusions 1 and 5) collected immediately
 after end of infusion (time recorded), then 15, 30, 45, 60, 90, 120, 180, and 240 minutes
 after the completion of the infusion.
 - 15-minute IV infusion of SL-401 at required dose.
 - Vital signs: immediately after completion of infusion and 30, 60, and 240 minutes postinfusion
 - Monitoring for at least 4 hours.
 - AE and SAE monitoring.

- If infusions are held (postponed) for any reason, an immunogenicity sample must be collected within 3 ± 3 days after completion of the last SL-401 infusion for the cycle.
- 9.2.3 Day 8 ±3 Days, or 3 ±3 Days after completion of infusions if infusion(s) held
 - Vital signs and weight.
 - Clinical laboratory tests: hematology and serum chemistry.
 - AE and SAE monitoring.
 - Concomitant medication assessment.
- 9.2.4 Day 15 ±3 Days
 - Vital signs and weight.
 - Clinical laboratory tests: hematology and serum chemistry.
 - AE and SAE monitoring.
 - Concomitant medication assessment.
- 9.2.5 Day 22 ±3 Days
 - Vital signs and weight.
 - Pregnancy test for FCBP within 7 10 days prior to initiation of POM in Cycle 1 (see Section 8.9 and Table 13).
 - Clinical laboratory tests: hematology and serum chemistry.
 - AE and SAE monitoring.
 - Concomitant medication assessment.
- 9.2.6 Cycle Delay
 - If Cycle 1 is delayed end of cycle evaluation for toxicity resolution if required Day 28 ±3 days, then every 7 ±3 days.
 - Concomitant medication assessment.
 - ECOG performance status.
 - Vital signs and weight.
 - Clinical laboratory tests: hematology, serum chemistry (including albumin)

AE and SAE monitoring

9.3 Cycles 1 through 6 combination therapy (Phase 1 and 2)

- 9.3.1 Days 1 5 (Up to Day 10 if Infusion(s) Held): Pre-infusion
 - Inpatient admission or treatment at a suitable outpatient facility.
 - Physical examination (complete physical examination on Day 1; symptom-directed on other days, as warranted).
 - ECOG performance status (Day 1 only).
 - Vital signs and weight.
 - 12-lead ECG (Day 1 only of each cycle).
 - Pregnancy test for FCBP within 24 hours prior to initiation of POM.
 - Clinical laboratory tests: hematology and serum chemistry (Day 1 of each cycle).
 - PT or INR/aPTT.
 - Urinalysis (Day 1 only of each cycle).
 - Extramedullary disease evaluation according to IMWG criteria (if needed to confirm response).
 - BM aspiration (if needed to confirm response).
 - Collection of blood (whole blood, serum, plasma) for correlative studies; Phase 1: Day 1
 of Cycles 1, 3 and 5. Phase 2: Day 1 of Cycles 2, 4, and 6.
 - Collection of peripheral blood for immunogenicity (serum) If infusions are held (postponed) for any reason, an immunogenicity sample must be collected within 3 ± 3 days after completion of the last SL-401 infusion for the cycle.
 - MM-specific laboratory tests (Day 1 only a -7 day window is permitted for scheduling).
 - PK sampling; phase 1 only (Cycle 2 only, infusions 1 and 5) prior to and following infusion.
 - Diphenhydramine 50 mg IV 60 minutes prior to infusion.
 - Acetaminophen 650 mg PO 60 minutes prior to infusion.

- Methylprednisolone 50 mg IV (or an equivalent dose of another corticosteroid)
 60 minutes prior to infusion.
- Ranitidine 50 mg IV (or an equivalent doses of another H₂-histamine antagonist)
 60 minutes prior to infusion. Days 1 5 (up to Day 10 if infusion(s) held): infusion 15-minute IV infusion of SL-401 at required dose.
- POM administration (Days 1 21) (POM to be administered 4 6 hours post infusion on the day of infusion 1 and 5 of Cycle 2).
- DEX administration (Days 1, 8, 15 and 22) (DEX to be administered 4 6 hours post infusion on the day of infusion 1 of Cycle 2).
- Vital signs: immediately after completion of infusion and 30, 60, and 240 minutes postinfusion.
- Monitoring for at least 4 hours.
- AE and SAE monitoring. Concomitant medication assessment.

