Grade 1 or 2 non-hematologic A/E, regardless of drug attribution, do not require dose modifications, unless in the opinion of the Investigator, the event is intolerable and warrants dose modification in consultation with the Medical Monitor.

SL-401 Adverse events that require holding SL-401 (all treatment cycles)

Heart rate ≥ 130 or ≤ 40 bpm	Investigate and address potential etiologies of tachy/bradycardia.
Systolic BP ≥ 160 or ≤ 80 mmHg	Hypertension : administer antihypertensive therapy as appropriate. Hypotension : evaluate potential capillary leak syndrome; administer parenteral hydration/electrolyte support as appropriate (refer to Section 7.7.3.3).
Serum creatinine > 2.0 mg/dL	Evaluate potential etiologies of renal dysfunction; parenteral hydration/electrolyte support as appropriate.
Serum albumin < 3.0 g/dL	Evaluate potential capillary leak syndrome. Administer parenteral (IV) albumin as indicated in protocol Section 7.7.3.3. Withhold subsequent SL-401 for the duration of the cycle.
Reduction in serum albumin by more than 1.0g/dL below level at the start of the current cycle (i.e. from 4.3g/dL to 3.2g/dL)	Evaluate potential capillary leak syndrome. Administer parenteral (IV) albumin as indicated in protocol Section 7.7.3.3. Withhold subsequent SL-401 for the duration of the cycle.
AST $> 5 \times$ the ULN or ALT $> 5 \times$ the ULN	Ongoing observation of clinical, laboratory and other parameters of hepatic dysfunction. Withhold subsequent SL-401 for the duration of the cycle.
Body temperature ≥ 38°C	Evaluate potential etiologies of fever, including infectious complications. Administer anti-pyretic therapy (i.e., acetaminophen/paracetamol) as appropriate.

CTCAE Category	Agents	Toxicity During a Cycle
Increase in body weight by \geq 1.5 kg over weight (pretreatment) on the prior treatment day.		Evaluate potential capillary leak syndrome. Evaluate for fluid retention or other potential etiologies of weight gain. Diuresis as appropriate.

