7.7.2.2 Procedures Required During Dosing Period

During each cycle, the following testing and procedures are required:

Vital Signs: Blood pressure, heart rate, respiration rate, body temperature, and pulse oximetry during dosing period (usually Days 1, 2, 3, 4 and 5) and Days 8, 15, and 22. Heart rate (HR), temperature, respiratory rate (RR), blood pressure (BP) to be taken pre- SL-401 infusion, at end of SL-401 infusion, every 30 minutes for 4 hours following the end of infusion and as clinically indicated for all doses of the Run-in Cycle. For Cycle 1 and thereafter, vital signs are to be taken pre-infusion, at end of infusion and as clinically indicated. For temperature > 38°C, obtain blood cultures (2 sets) and collect urine for urinalysis and culture.

Diagnostic Tests:

- During dosing period, prior to SL-401 infusion (usually Days 1, 2, 3, 4, 5) and Days 8, 15, and 22: complete blood count (CBC) with differential, platelets, sodium, potassium, chloride, bicarbonate, blood urea nitrogen (BUN), creatinine, glucose, total protein, albumin, calcium, phosphorus, uric acid, total bilirubin, ALT, AST, alkaline phosphatase, lactate dehydrogenase (LDH), CPK, prothrombin time (PT) / International Normalized Ratio (INR), and partial thromboplastin time (PTT).
- Days 1 (prior to SL-401 infusion): routine urinalysis
- For temperature ≥ 38°C, draw blood culture × 2, and collect urine for urinalysis and culture/
- Daily weight (during the period of the 5 infusions) and Days 8, 15 and 22.

The results of these evaluations may result in withholding of a scheduled SL-401 infusion, largely based on unresolved manifestations of fluid retention and/or other relevant acute toxicities during daily dosing, are described below and in Table 11.

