7.7.3.3 Capillary Leak Syndrome

Capillary leak syndrome is associated with vascular endothelial injury related to fusion protein administration and may occur 3 – 8 days after initiation of treatment. Patients may exhibit symptoms of hypotension, weight gain, edema, nausea, and anorexia, shortness of breath and, at

times, confusion and muscle injury. Findings may include hypoalbuminemia, reductions in blood oxygen saturation, and evidence of pulmonary edema on chest x-ray. Patients with hypotension will receive 500 cc normal saline boluses and observation as detailed in Section 7.7.3.2. Patients will have serum albumin measurements daily until completion of SL-401 administration and will receive 25 g albumin IV each day the serum albumin is < 3 g/dL. Patients with > 10% weight gain and no hypotension may be treated with fluid restriction and/or diuretics such as furosemide as clinically indicated per Investigator discretion.

As indicated above in the setting of delays secondary to findings consistent with capillary leak syndrome (i.e., in the setting of resolved hypotension, tachycardia, increased weight, or albumin reductions of a magnitude lower than those warranting withholding of SL-401 for the duration of a given cycle), subsequent SL-401 infusions are to be administered on days subsequent to the identification of the abnormality (not the same day), pending determination by the Investigator that there is no/minimal evidence of ongoing capillary leak syndrome and pending discussion with the study Medical Monitor.

In settings in which albumin is reduced to <3.0g/dL or in which albumin is reduced by more than 1.0 g/dL below the level at the start of the cycle (i.e. from 4.3g/dL to 3.2g/dL), no subsequent SL-401 will be administered for the duration of the cycle.

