8.8 Clinical Laboratory Tests

The following assessments should be done per the visit schedule and processed by the local laboratory:

- Hematology: Minimally, scheduled hematology collections should include white blood cell count, differential white cell count (lymphocytes, monocytes, basophils, eosinophils, neutrophils), red blood cell count, hematocrit, hemoglobin and platelet count.
- Serum albumin: May be a component of the serum chemistry panel. See Section 7.2.2 for administration of albumin if serum albumin decreases to < 3 g/dL during treatment days or in the immediate post-treatment period.
- Serum electrolytes and chemistry: Chemistry includes: glucose (fasting at baseline), albumin, total protein, AST, ALT, bilirubin (total and direct), alkaline phosphatase (AP), LDH, CPK, sodium, potassium, chloride, bicarbonate/carbon dioxide, calcium, magnesium, phosphate, uric acid, blood urea nitrogen (BUN), serum creatinine and estimated creatinine clearance (Cockroft-Gault formula; see Appendix 15.7). Albumin, transaminases (AST/ALT) and creatinine must be evaluated prior to each SL-401 dose.
- Coagulation parameters: PT and/or INR, aPTT.
- Urinalysis: Appearance, color, pH, specific gravity, ketones, leukocytes, protein, glucose, bilirubin, urobilinogen, and occult blood.

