9.7 Follow-Up

Patients who discontinue therapy for reasons other than MM progression will be followed for disease response every month until progression of disease or initiation of subsequent therapy. Patients who have discontinued study therapy and have had MM progression should be contacted approximately every 3 months (telephone contact is permitted) to assess survival status for up to one year; patients who discontinue therapy for reasons other than disease progression and are no longer willing to follow-up for evaluation of disease progression should also be contacted for survival status whenever feasible.

Table 13: Schedule of Events

	Screening/ Baseline	Run in Cycle Cycle is 28 days																	
Evaluation	D-21 to -1	D 1	D 2	D 3	D 4	D 5	D 8	D 15	D 22	D 1	D 2	D 3	D 4	D 5	D 8	D 15	D 22	EOT	F/Uw
Informed Consent & Pomalyst REMS ^a	х																		
Entry Criteria Review	Х											,							
Medical and Myeloma History	x																		
Physical Examination ^c	X	X	Х	Х	Х	Х	X	Х	Х	х	X	Х	Х	Х	Х	X	Х	X	
Performance Status (ECOG)	х	x								х								x	
Height (Baseline only) / Weight	х	x	х	х	х	х	x	х	х	х	х	х	х	х	х	х	х	х	
Vital Signs (HR, Temperature, RR, $\mathrm{BP})^{\mathrm{d}}$	x	X	x	х	х	х	x	x		х	х	x	x	x	x	x		x	
ECG	X									х								х	
ECHO/MUGA	х								77										
Pregnancy testing [FCBP) and counseling *	х								Xe	х					Xe	Xe	Xe	х	
Hematology	X	x	x	х	х	х	x	x	x	Xf	x	х	х	x	х	x	х	x	
Serum Chemistry®	X	X	X	Х	х	X	X	X	X	Х	х	Х	X	Х	X	X	Х	X	
PT / INR aPTT	х									х								x	
Urinalysis h	Х	X								х								х	
Plasmacytoma Evaluation ⁱ	x									Xi								x	As needed
Skeletal Survey j	X																		As needed
Bone Marrow Aspiration and biopsy ^k	х									Xk								х	
Peripheral blood for correlative studies ¹	x									Xl								x	

	Screening/ Baseline				Run ir ycle is					Cycles 1 - 6 ⁿ Each Cycle is 28 days									
Evaluation	D-21 to -1	D 1	D 2	D 3	D 4	D 5	D 8	D 15	D 22	D 1	D 2	D 3	D 4	D 5	D 8	D 15	D 22	ЕОТ	F/U ^w
Myeloma-specific Laboratory Tests ^m	x	х								х								х	As needed
PK (SL-401) ⁿ		Х				х				X C2				X C2				x	
Immunogenicity (SL-401)°		x				х				х								x	
SL-401 Pre-medication ^p		x	x	x	x	x				x	x	x	x	x					
SL-401 Administration ^q		х	X	Х	Х	Х				Х	X	х	х	Х					
Pomalidomide ^r										Days 1 - 21									
Dexamethasone										x					x	x	x		
Adverse Event monitoring ⁶	x		← X →							x									
Prior/Concomitant Medication ^t	x			← X →							x								

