- Informed consent All patients must sign an IRB approved informed consent prior to screening and agree to enroll in the Pomalyst REMS program prior to starting POM.
- b. Medical History: Includes relevant history of previous/associated pathologies other than the tumor. Myeloma History: Includes date of initial diagnosis, stage, and extent of the disease both at diagnosis and at study entry, previous anti-tumor therapy (including surgical, radiation and systemic therapy; for systemic therapy, includes approximate dates of administration, best response and approximate dates of disease progression).
- c. Physical Examination: Consists of examination of major body systems including neurologic, digestive, respiratory, any evaluable sites of extramedullary disease. Physical examination is required at screening/baseline and Day 1 of each treatment cycle. Symptom directed physical examination may also be performed on other treatment days or mid-cycle evaluations if there are symptoms or vital sign abnormalities warranting examination.
- d. Vitals signs: HR, temperature, RR, BP, and pulse oximetry to be taken pre- SL-401 infusion, end of SL-401 infusion, every 30 minutes for 4 hours post end of infusion and as clinically indicated for all doses of the Run-in Cycle. Cycle 1 +, vital signs are to be taken pre-infusion, at end of infusion and as clinically indicated. For temperature ≥ 38°C, draw blood cultures ×2 and collect urine for urinalysis and culture.
- e. **Pregnancy tests** for FCBP at screening, test must be repeated within 10 14 days prior to initiation of POM therapy (before Cycle 1) and again within 24 hours prior to initiation of POM therapy (before Cycle 1). While on POM, repeat pregnancy test every week for the first 4 weeks and then every 28 days while on therapy and during interruptions in therapy and 28 days following discontinuation of POM. Women with irregular menstruation must have pregnancy testing every 14 days while on therapy and during interruptions and 14 and 28 days after discontinuation of POM. All patients enrolled into this study, must be registered in and must comply with all requirements of the POMALYST REMSTM program. A FCBP is a female of childbearing potential is a sexually mature woman who: 1) has not undergone a hysterectomy or bilateral opphorectomy; or 2) has not been naturally postmenopausal for at least 24 consecutive months.

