- Hematology: CBC to be performed and reviewed by clinician prior to SL-401 dosing on Days 1 5 and Days 8, 15 and 22 or as clinically indicated. The Run in and Cycle
 1, Day 1, results must remain within the entry criteria values to initiate therapy.
- g. Serum Chemistry: to be performed and reviewed by clinician prior to SL-401 dosing on Days 1 5 and Days 8, 15, and 22 or as clinically indicated. The Run in and Cycle 1 Day 1 results must remain within the entry criteria values to initiate therapy. Chemistry includes: glucose (fasting at baseline), albumin, total protein, AST, ALT, bilirubin

- (total and direct), alkaline phosphatase, LDH, CPK, sodium, potassium, chloride, bicarbonate/carbon dioxide, calcium, magnesium, phosphate, uric acid, BUN, serum creatinine and estimated creatinine clearance (Cockroft-Gault formula Appendix 15.7). Albumin, transaminases (AST/ALT) and creatinine must be evaluated prior to each SL-401 dose.
- Urinalysis: Appearance, color, pH, specific gravity, ketones, leukocytes, protein, glucose, bilirubin, urobilinogen, and occult blood. To be performed at baseline, during the treatment period as clinically indicated and EOT.
- i. Plasmacytoma Assessment Disease: For patient with known or suspected plasmacytomas, assess by physical exam and/or radiologic evaluation at baseline and as clinically indicated. Disease that can be assessed by physical exam should be evaluated on Day 1 of each cycle. Disease that can be assessed by radiologic evaluation should be assessed according the IMWG criteria for evaluation of response. This may include computerized tomography (CT) scan, ultrasound, PET/CT or MRI. The same method of assessment should be used at each evaluation for any individual patient. Assess the need to evaluate for suspected new, worsening, or improved plasmacytomas to confirm response or progression every cycle. Evaluations may be performed on Day 1 of a cycle or during the 7 days prior to Day 1 of the Cycle as needed for scheduling.
- j. Skeletal Survey: Plain film X-rays to including skull, vertebrae, all long bones, pelvis and chest are required. PET/CT MRI may be done to supplement X-rays of any disease site at Investigators discretion. Also required at any time when clinically indicated, for suspected progression per IMWG response criteria.

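### Three schedule items to align: the Section 9.3.1 lab line, the pre-pomalidomide pregnancy-test window, and post-infusion vital signs for phase 2 patients who have no run-in

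*Protocol*

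**What the plan says.** **Labs.** Section 9.3.1 is the pre-infusion list for Days 1–5 of Cycles 1–6. Its lab line reads "Clinical laboratory tests: hematology and serum chemistry (Day 1 of each cycle"). Elsewhere:

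- Section 7.7.2.2, which covers each cycle, asks for the blood count and chemistry "prior to SL-401 infusion (usually Days 1, 2, 3, 4, 5) and Days 8, 15, and 22".
- Section 7.7.3.3: "Patients will have serum albumin measurements daily until completion of SL-401 administration".
- Section 8.8: "Albumin, transaminases (AST/ALT) and creatinine must be evaluated prior to each SL-401 dose".
- Table 13 note g: "Serum Chemistry: to be performed and reviewed by clinician prior to SL-401 dosing", on Days 1–5. Note f says the same for the blood count.
- The Table 13 grid marks the row "Serum Chemistry" on each of D1 to D5 of Cycles 1–6.

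Table 11 heads the relevant holds "SL-401 Adverse events that require holding SL-401 (all treatment cycles").

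**Pregnancy test before pomalidomide (POM).** Inclusion criterion 9 (Section 5.2 and synopsis), Section 10.4 and Table 13 note e put the earlier of the two tests 10–14 days ahead. Sections 8.9 and 9.2.5 put it 7–10 days ahead. Section 9.2.5 and the Table 13 grid place it at the run-in Day 22 visit.

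**Vital signs.** Table 13 note d sets readings "every 30 minutes for 4 hours post end of infusion and as clinically indicated for all doses of the Run-in Cycle", and Section 7.7.2.2 agrees. From Cycle 1, both require only a pre-infusion and an end-of-infusion reading, plus others if clinically indicated. Sections 9.2.2 and 9.3.1 give end of infusion, 30, 60 and 240 minutes, for the run-in and for Cycles 1–6 alike. Section 6.2.4 drops the run-in from phase 2, assesses the first 6 such patients for DLT, and allows the run-in to be brought back if more than one of them has a DLT.

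**The concern.** The lab holds depend on values that change during the five dosing days. One albumin hold is a fall of more than 1.0 g/dL from the level at the start of the cycle, which a Day 1 sample cannot show. Section 7.7.3.3 places capillary leak 3–8 days after the start of treatment. A site working from the Section 9.3.1 visit list alone would dose on Days 2–5 without the results that the holds require.

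The two pregnancy-test windows bear on eligibility and fetal safety for a drug under a mandatory REMS programme. Section 9.2.5 sends the site to Section 8.9 and to Table 13, and these disagree. A woman of childbearing potential tested on the nominal Day 22 meets Sections 8.9 and 9.2.5 but fails inclusion criterion 9.

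The half-hourly readings appear meant for first exposure to SL-401. In phase 2, first exposure is already in combination with POM and dexamethasone, in the cycle in which the first 6 patients are assessed for DLT. Because the rule names the run-in, it does not reach them.

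**Working it through.** There is no plan figure to reproduce. The check compares the schedule texts and counts.

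**1. Labs**

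- Infusions in Cycles 1–6: 6 cycles × 5 = 30.
- Pre-infusion panels named by Section 9.3.1 read alone: 6 × 1 = 6.
- Panels required by Sections 7.7.2.2 and 8.8 and by Table 13: 6 × 5 = 30.
- Difference: 30 − 6 = 24. This is the gap in the Section 9.3.1 line, not in the protocol as a whole. Section 9.3.1 is the only place that differs.

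**2. Pregnancy test (patients with a run-in)**

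A 28-day run-in with no delay puts Cycle 1 Day 1, the first POM dose, on run-in Day 29.

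| Item | Run-in days |
|---|---|
| 10–14 days before POM | 29 − 14 = 15 to 29 − 10 = 19 |
| 7–10 days before POM | 29 − 10 = 19 to 29 − 7 = 22 |
| Day 22 ±3 visit | 19 to 25 |
| Day 15 ±3 visit | 12 to 18 |

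- The two windows share only Day 19.
- The Day 22 ±3 visit meets 10–14 days on Day 19 alone. Days 23–25 are 6 to 4 days before POM and meet neither window.
- The Day 15 ±3 visit meets 10–14 days on Days 15–18.
- With a one-week delay (Section 7.8), Cycle 1 starts on Day 36 and 10–14 days before is Days 22–26. A test on Days 15–19 would then be 36 − 15 = 21 to 36 − 19 = 17 days before POM, so it would need repeating.
- A phase 2 patient without a run-in can have this test in screening (Day −21 to −1), where 10–14 days fits.

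**3. Fixed vital-sign readings after the end-of-infusion one**

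| First SL-401 exposure | Governing text | Per infusion | Per 5 infusions | Longest gap |
|---|---|---|---|---|
| Phase 1 run-in | 7.7.2.2, note d | 240/30 = 8 | 8 × 5 = 40 | 30 min |
| Phase 2 Cycle 1, no run-in | 9.3.1 | 3 (30, 60, 240 min) | 3 × 5 = 15 | 240 − 60 = 180 min |
| Phase 2 Cycle 1, no run-in | 7.7.2.2, note d | 0 | 0 | none fixed |

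- The half-hourly times contain 30, 60 and 240 minutes, so the schedules nest. A site using the fuller one in each cycle complies with every section.
- Difference from Section 9.3.1: 40 − 15 = 25 readings per patient in Cycle 1.
- Patients affected: 14 of the 20 at the phase 2 dose (70%) if the run-in stays out. If it is reinstated after the first 6, as few as 6 of 20 (30%).

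**The case against.** **Labs.** Five other places state the stricter rule, and Section 8.8 makes it mandatory. The Section 9.3.1 line is not even worded as exclusive: ECG and urinalysis in the same list are restricted to Day 1 only, while the lab line merely names Day 1. Day 1 also has its own role, since Table 13 notes f and g require Cycle 1 Day 1 results to stay within the entry criteria. All of this stands, and it makes the line a drafting slip. A reader might set it beside Section 9.2.1, which has no Day 1 limit, and infer a deliberate step-down that leaves 24 infusions unchecked. The documents do not support that: Section 7.7.2.2 applies to each cycle, and the grid marks all five days in Cycles 1–6.

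**Pregnancy test.** An undelayed patient tested on Day 19 satisfies every section, the grid mark points to note e for its timing, and every version repeats the test within 24 hours of POM. So it would be too strong to say that compliance is impossible, or that the problem reaches patients without a run-in. The conflict at the nominal visit day remains.

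**Vital signs.** Reducing scheduled readings after the run-in is a choice the protocol may make, and phase 2 uses a dose already evaluated in at least 6 patients (Section 6.2.3). A reader might infer that phase 2 first exposure goes unmonitored. It does not: at least 4 hours of monitoring, the inpatient first cycle (Section 7.3.2.4) and readings when clinically indicated all still apply. Only the fixed readings differ. Nor is 14 of 20 certain, given the reinstatement clause in Section 6.2.4. What stands is that Section 7.3.2.4 ties the inpatient rule to the first SL-401 cycle, whether single agent or combination, and the vital-sign rule was not adapted in the same way.

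**Conclusion.** The point holds as a set of low-severity consistency and safety corrections. It has no bearing on power, error rates or endpoints.

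- **Labs:** Section 9.3.1 is wrong as written and names 1 of the 5 infusion days. The tests themselves are scheduled elsewhere, so no test is missing from the protocol.
- **Pregnancy test:** this is a genuine conflict. For patients with a run-in and no delay, only Day 19 of the Day 22 ±3 visit meets the inclusion criterion. This assumes a 28-day run-in with POM starting on Day 29.
- **Vital signs:** this is a cheap improvement rather than an error. There are at most 3 fixed readings per infusion after the end-of-infusion one, against 8 in the run-in. It affects all 14 planned phase 2 patients, or as few as the first 6 if the run-in is reinstated.

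**What to change.** 1. **Labs.** Change the Section 9.3.1 line to: *before each SL-401 infusion, and Day 1 of each cycle*. This adds no draws beyond the Table 13 grid.
2. **Pregnancy test.** Use 10–14 days throughout. Move the run-in test to Days 15–19 by editing Sections 8.9, 9.2.4 and 9.2.5 and the Table 13 grid. Repeat it if a Cycle 1 delay puts it outside the window. State that phase 2 patients without a run-in are tested within screening. The cost is one repeat test for a woman of childbearing potential whose Cycle 1 is delayed.
3. **Vital signs.** In Sections 7.7.2.2, 9.2.2 and 9.3.1 and Table 13 note d, change the post-infusion readings only: *end of infusion, then every 30 minutes for 4 hours in the patient's first SL-401 cycle (run-in, or Cycle 1 if there is no run-in); end of infusion, 30, 60 and 240 minutes thereafter*. Keep the pre-infusion reading, on which the heart-rate, blood-pressure and temperature holds rely, and keep the provision for further readings when clinically indicated. Compared with Section 9.3.1, the cost is 25 extra scheduled readings per affected patient in Cycle 1: 25 × 14 = 350 at most, or 25 × 6 = 150 if the run-in returns after the first 6. Later cycles need none beyond Section 9.3.1.
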